9.1 General Methods

All analyses for this exploratory study will be done by using appropriate descriptive statistics by study group. All results will be summarized in tables. Patient individual data will be provided in Listings. No graphs are envisaged for this study.

For **continuous variables**, the mean, standard deviation, minimum, median and maximum will be presented, together with the total number of observations and the number of missing and non-missing values. Unless otherwise specified minimum and maximum values will be reported to the same number of decimal places as the recorded measurements, mean and median are reported to one more decimal place and standard deviation one additional decimal place more than the mean.

For **categorical variables**, absolute and relative frequencies will be reported. Relative frequencies will be based on all observations and reported as a percentages to one decimal place. Unless otherwise specified percentages will be based on the number of patients in considered analysis set including also percentages for missing categories. Only categories with non-null values will be presented in summary tables.

Incidences like adverse events, medical histories and concomitant medications will be reported on a subject basis. The percentages will be calculated using the number of patients in the considered analysis data set.

9.2 Specific Methods for Efficacy Analyses

As a general principle, all secondary efficacy analyses will be performed for the study eye only. Efficacy data in non-study eye will be listed.

For the primary and secondary endpoints, mean change from baseline will be compared between treatment groups for the study eye. The null hypothesis will be tested that there is no difference between rhNGF and vehicle in the mean overall change from baseline between both treatments:

$$H_0: \mu_{\text{rhNGF}} = \mu_{\text{Vehicle}}$$

$$H_1: \mu_{\text{rhNGF}} \neq \mu_{\text{Vehicle}}$$

Where μ is the mean change from baseline at considered visit within the given treatment.

This hypothesis will be tested exploratory at a 5% level of significance with an Analysis of the Covariance (ANCOVA) with treatment and respective baseline value in the model. The Least-squares means estimate of the treatment effect and the treatment group difference (both with 95% confidence intervals) will be reported. P-values will be rounded to three decimal places. If a p-value is less than 0.001 it will be reported as "<0.001". Due to the high numbers of observations, the assumption of normality is assumed.

The analysis will be performed for the following endpoints:

- Change from Baseline in Sande Frequency and Severity Score at Week 8 (LOCF) for the FAS as exploratory primary efficacy analyses
- Change from Baseline in Sande Frequency and Severity Score at Week 8 (LOCF) for the PPS as supportive to primary efficacy analyses

- Change from Baseline in Sande Frequency and Severity Score (without imputation) at Week 4, Week 8 and Week 12 for the FAS as supportive to primary efficacy analyses
- Change from Baseline in Corneal and Conjunctival staining at Week 4, Week 8 and Week 12 for the FAS as well as PPS as exploratory secondary efficacy analyses
- Change from Baseline in TFBUT at Week 4, Week 8 and Week 12 for the FAS as well as PPS as exploratory secondary efficacy analyses
- Change from Baseline in Wetting Distance (5 minutes) at Week 8 for the FAS as well as PPS as exploratory secondary efficacy analyses.

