Analyses of endpoints will be performed based on evaluations obtained on days 0, 28±2, 56±4 and 28±4 days after discontinuation of study treatment. Details of analyses will be presented in the Statistical Analysis Plan finalized before Database Lock.

Sample size calculation

Sample size was calculated by assuming both for severity and frequency a mean difference from baseline SANDE scores of -30±20 in the rhNGF groups versus -20±20 in vehicle group (80% power, alpha =0.05; 2-sided test), considering that the active compound has already proven safe

and effective in dry eye patients. The sample size has been calculated based on a 2:1 randomization scheme by the following formula:

$$n_1 = (0.5) \times n \times (1 + k)$$

$$n_2 = (0.5) \times n \times (1 + (1/k))$$

With n_1 = active treatment, n_2 = vehicle, $n = 63$, and $k = n_1/n_2 = 2/1=2$. Therefore, $n_1 = 94.5$ and $n_2 = 47.25$. Assuming a 5% dropout rate, a total of 100 patients will be enrolled in the active arm, and 50 in the vehicle arm.

Study procedures				
Study procedures	Baseline Visit Day 0	Week 4^a	Week 8^b	Follow-up Visit Week 12 or early termination^b
Informed Consent	X			
Inclusion/Exclusion Criteria	X			
Urine Pregnancy Test	X		X	
Randomization	X			
Demographics	X			
Ocular and General Medical History	X			
Previous and Concomitant Ocular And Systemic Medications	X	X	X	X
Frequency of Artificial Tear Use	X			X
Record Adverse Events (AEs)	X	X	X	X
Verify Patient Study Medication Dosing Compliance		X	X	
SANDE ^c questionnaire	X	X	X	X
Best Corrected Distance Visual Acuity (BCDVA)	X	X	X	X
Schirmer test I (without anesthesia)	X		X	
External Ocular Examination	X	X	X	X
Slit-lamp Examination (SLE)	X	X	X	X
Fluorescein and lissamine green staining (NEI scale)	X	X	X	X
Tear Film Break-up Time (TFBUT)	X	X	X	X
InflammaDry (MMP-9)	X		X	
Study Drug Dispensation	X	X		

a.) Visit window of ± 2 days; b.) Visit window of ± 4 days; c.) SANDE - Symptom Assessment In Dry Eye

TABLE OF CONTENTS

	Page	
1	INTRODUCTION	16
1.1	Background Information	16
1.1.1	Nerve growth factor - overview	16
1.1.2	Chemical and formulation data	16
1.1.3	Rationale for rhNGF therapy in patients with dry eye	16
1.1.4	Previous experience in humans with rhNGF	17
1.2	Study Rationale	18
1.2.1	Dose and Schedule Rationale	18
1.3	Risks and benefits	19
2	STUDY OBJECTIVES	20
2.1	Primary endpoint	20
2.2	Secondary endpoints	20
2.3	Exploratory endpoint	20
2.4	Safety endpoint	20
3	CLINICAL SUPPLIES	21
3.1	Treatment	21

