4.2 Study Design

This is a Phase II, single-center, randomized, double-masked, parallel-arm, vehicle-controlled trial, designed to evaluate the safety and efficacy of rhNGF eye drops at 20 µg/ml concentration administered six times daily for 8 weeks in patients with dry eye.

Eligible patients will be randomized 2:1 to either rhNGF eye drops 20 µg/ml (100 patients) or vehicle (50 patients) six times daily and treated for 8 weeks.

Before randomization the study eye will be determined for primary efficacy and safety analysis as the “worse eye” (i.e. the eye with more severe dry eye – if both eyes are equally worse, the right eye will be the study eye). In all patients, both eyes will be treated as specified below:

Group 1: rhNGF 20 µg/mL: *One drop (40 µL) corresponding to 0.80 µg of rhNGF will be instilled into each eye six times a day (every 2h), for a total daily dose of 9.6 µg.*

Group 2: Vehicle: *One drop (40 µL) will be instilled into each eye six times a day (every 2h).*

[figure not shown]
Administration of rhNGF six times daily will maintain and improve lubrication of the ocular surface since the use of preservative-free artificial tears will not be allowed during treatment period.

In the 4 weeks following the end of the study treatment, no further treatment will be allowed, except preservative-free artificial tears (use recorded in drops/day).

Drop-Outs after randomization will not be replaced.

The study flow chart is given below:

Figure 4.2.1 Study flow chart

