4.6 Sample Size estimation

Sample size was calculated by assuming both for severity and frequency a mean difference from baseline SANDE score of -30 ± 20 in the rhNGF groups versus -20 ± 20 in vehicle group (80% power, $\alpha = 0.05$; 2-sided t-test), considering that the active comparator has already proven safe and effective in dry eye patients.

Testing hypotheses are:

H0: mean change from baseline rhNGF = mean change from baseline Vehicle = 0

H1: mean change from baseline rhNGF = mean change from baseline Vehicle = -10

Therefore, the sample size has been calculated based on a 2:1 randomization scheme for inference with Student t test for independent groups using PS Power and Sample Size Calculations (<http://biostat.mc.vanderbilt.edu/PowerSampleSize> Version 3.0, January 2009 Copyright © 1997-2009 by William).

If the true difference in the experimental and control means is 10 (estimated from our internal study), we will need to study 96 experimental subjects and 48 control subjects to be able to reject the null hypothesis that the population means of the experimental and control groups are equal with probability (power) 0.8 and with standard deviation of 20. The Type I error probability associated with this test of this null hypothesis is 0.05.

Considering a 5% drop out, 150 patients will be included in the study: 100 patients in rhNGF group and 50 patients in vehicle group.

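### SAP 9.2 implies one residual variance under 2:1 allocation: if the arms' SDs differ, the 95% CIs miss their stated coverage, and one SAP sentence would prevent this

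*SAP*

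**What the plan says.** SAP 9.2 compares mean change from baseline between arms at the 5% level "with an Analysis of the Covariance (ANCOVA) with treatment and respective baseline value in the model". Least-squares means and their difference are reported with 95% confidence intervals. The same model serves SANDE frequency and severity, corneal and conjunctival staining, TFBUT and Schirmer wetting distance. The section assumes normality on the ground of the large number of observations. It does not mention equality of variances, a robust standard error or an unequal-variance sensitivity analysis.

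On allocation, SAP 4.2 states: "Eligible patients will be randomized 2:1 to either rhNGF eye drops" or vehicle, as 100 and 50 patients. SAP 4.6 plans for "inference with Student t test for independent groups", with 96 and 48 patients, "with probability (power) 0.8 and with standard deviation of 20", and a difference of 10. The protocol (synopsis and section 10.2) attaches the same SD of 20 to the assumed change in each arm, for SANDE severity and frequency. Neither document gives an SD for any other endpoint.

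SAP 4.7 and 9.2.1.3 describe all inference as exploratory, without adjustment for multiplicity.

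**The concern.** An ordinary ANCOVA estimates one residual variance from both arms together. With arms of equal size, the resulting standard error of the difference is right on average even if the SDs differ. With 2:1 allocation it is not. The pooled variance mostly reflects the rhNGF arm, whereas the true variance of the difference depends most on the smaller vehicle arm. Intervals come out too narrow if vehicle is the more variable arm and too wide if rhNGF is.

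The SAP's appeal to a large number of observations answers the normality question only. More patients at the same ratio leave the ratio of estimated to true standard error unchanged.

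At stake is whether the reported 95% intervals for the treatment difference mean what they say. In the case where rhNGF is more variable, some power is also lost. These intervals and p-values are the plan's only between-arm inference. Counting scores, visits and analysis sets, SAP 9.2 lists 30 such contrasts: 10 for SANDE, 12 for staining, 6 for TFBUT and 2 for Schirmer.

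**Working it through.** **Inputs from the documents.** Two-sided alpha 0.05, power 0.80, difference 10, SD 20 in both arms, allocation 2:1, 96 and 48 evaluable patients (SAP 4.6); ANCOVA with treatment and baseline (SAP 9.2). All SD pairs other than 20/20 are assumptions, shown as a range.

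**The plan's own figure.** Vehicle n = (1 + 1/2) × 20² × (1.960 + 0.842)² / 10² = 6 × 7.85 = 47.1, rounded up to 48, so rhNGF n = 96. This agrees with SAP 4.6. Exact t-test power at 96/48 is 80.2%.

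**Estimated and true standard errors.** With n1 = 96 (rhNGF, SD s1) and n2 = 48 (vehicle, SD s2), ignoring the small baseline term:

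- pooled variance = (95·s1² + 47·s2²) / 142
- pooled SE = √[pooled variance × (1/96 + 1/48)]
- true SE = √[s1²/96 + s2²/48]
- approximate coverage = 2Φ(t × pooled SE / true SE) − 1, with t the 97.5% point on 141 df, about 1.977

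For SDs 20/25: pooled variance = (38,000 + 29,375)/142 = 474.5; pooled SE = √(474.5 × 0.03125) = 3.851; true SE = √(4.167 + 13.021) = 4.146; ratio 0.929; coverage about 93.4%.

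For 25/20: pooled SE = √(550.5 × 0.03125) = 4.148; true SE = √(6.510 + 8.333) = 3.853; ratio 1.077; coverage about 96.7%.

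With the same 144 patients split 72/72, the two standard errors coincide for every SD pair. The 2:1 ratio is therefore what exposes the between-arm comparison.

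**Simulation of the SAP's ANCOVA** (normal residuals, common baseline slope; 100,000 runs for coverage and 60,000 for power at a difference of 10). The SDs are residual SDs. Coverage is one minus the rejection rate with no mean difference, because coverage does not depend on the true difference. The separate-variance analysis keeps the least-squares estimate and uses arm-specific variances with Satterthwaite df.

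| rhNGF SD / vehicle SD | SE ratio | Coverage, one variance | Coverage, separate | Power, one variance | Power, separate | Half-width, one / separate |
|---|---|---|---|---|---|---|
| 20/20 | 1.000 | 95.1% | 95.1% | 80.1% | 79.7% | 7.00 / 7.04 |
| 20/22 | 0.969 | 94.2% | 95.0% | 76.6% | 74.3% | 7.24 / 7.52 |
| 22/20 | 1.032 | 95.7% | 95.0% | 75.1% | 76.7% | 7.48 / 7.27 |
| 20/25 | 0.929 | 93.3% | 95.1% | 71.6% | 66.3% | 7.62 / 8.26 |
| 25/20 | 1.077 | 96.5% | 95.2% | 68.0% | 73.0% | 8.21 / 7.65 |
| 20/30 | 0.878 | 91.6% | 95.0% | 63.5% | 53.7% | 8.32 / 9.55 |
| 30/20 | 1.139 | 97.4% | 95.1% | 54.7% | 65.0% | 9.49 / 8.36 |

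Coverage at 100/50 agrees within about 0.1 point. A smaller simulation with HC3 standard errors (20,000 runs, SDs 20/25, 20/30, 25/20 and 30/20) gave rejection rates of 4.6% to 4.8%, that is, coverage of 95.2% to 95.4%.

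**Arm-specific least-squares means.** SAP 9.2 also gives these an interval. At 20/25 the pooled SD is √474.5 = 21.8. Coverage is about 91.5% for vehicle and 96.9% for rhNGF, ignoring the baseline term.

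**The case against.** The strongest reply is that nothing in the documents indicates unequal SDs. The only values are 20 and 20, and every unfavourable row above is assumed. This stands. The mechanisms one might cite also pull in opposite directions: a mix of responders and non-responders would widen the rhNGF arm, while a floor on a bounded scale would narrow it. The documents do not say which arm would be more variable.

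A reader might infer that the type I error is inflated to 6.7% or 8.4% (the 20/25 and 20/30 rows). The documents do not support that reading. In a randomised trial of a drug that does nothing, both arms share one distribution and the pooled test is valid. Those rates need a drug that changes the spread but leaves the mean alone. The argument that holds concerns interval coverage and power when there is a real effect.

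A further reply is that the plan is exploratory: Protocol 10.2 calls the analysis descriptive, and SAP 4.7 adds inference only at the sponsor's request. This lowers the stakes, since no confirmatory claim depends on these tests. It does not dispose of the point, because waiving multiplicity adjustment is different from accepting that a reported 95% interval covers something other than 95%.

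Finally, SDs are tabulated by arm (SAP 9.1, 10.5.1, 10.5.2), so unequal spread would be visible. That limits the harm, but it becomes visible only after unmasking, when changing the model would be post hoc.

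**Conclusion.** The point holds as a conditional one of minor severity. If the residual SDs differ between arms, the 2:1 design makes the single-variance ANCOVA's intervals and p-values miscalibrated, in a direction that depends on which arm is more variable. Coverage moves by less than a point with a 10% SD difference, by about 1.5 to 1.7 points with a 25% difference, and by up to about 3.4 points with a 50% difference. The power loss at 25/20 is 73.0 − 68.0 = 5.0 points.

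These sizes rest on normal residuals, a common baseline slope, 96/48 evaluable patients and the assumed SD pairs. Coverage depends on the ratio of the SDs; the powers and half-widths also depend on their level. That a single variance is used is inferred from the model named, since the SAP does not state it.

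A reader might go further and conclude that all the efficacy intervals and p-values are wrong. The documents do not support this: under their own equal-SD assumption the ANCOVA is correctly calibrated, and the treatment estimates are unbiased in either case. Nor is the remedy entirely free, as the 20/20 row shows.

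**What to change.** Add one sentence to SAP 9.2 before unmasking. For all listed endpoints, either estimate the residual variance separately by treatment arm, with Satterthwaite or Kenward-Roger degrees of freedom (for example PROC MIXED with REPEATED / GROUP=treatment), or use HC3 standard errors. Make this the main model or, at minimum, a pre-specified sensitivity analysis.

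The cost is one option in the code. If the SDs are equal, power falls from 80.1% to 79.7%, the half-width grows by about 0.5% (7.00 to 7.04), and mean df fall from 141 to about 95. If vehicle is more variable, intervals widen (8.26/7.62, about 8% at 20/25) and nominal power drops from 71.6% to 66.3%; this removes precision that was never there. A mixed model also reweights the common baseline slope, so its estimate can differ slightly from the ordinary ANCOVA; HC3 leaves the estimate unchanged. Under the documents' own assumptions the sample size need not change.

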9.2.1 Statistical/Analytical Issues

9.2.1.1 Adjustments for Covariates

Not alpha adjustment is envisaged, as all statistical hypotheses testing will be performed in an exploratory manner.

9.2.1.2 Handling of Dropouts or Missing Data

In the derivation of endpoints there will be no replacement of missing data except for primary endpoint Change from Baseline in Sande Frequency and Severity Score, age, time since initial diagnosis of Dry Eye disease, adverse event dates as well as concomitant medication dates. Details of applied imputations are described in the respective sections of chapter 8.2.

9.2.1.3 Multiple Comparisons/Multiplicity

Due to this being an exploratory study, no adjustment of any p-values will be made to account for inflation of the Type 1 error rate arising from multiple comparisons or multiple endpoint testing.

9.3 Specific Methods for Safety Analyses

As a generally principle, Adverse event data will be analyzed separately by study period (Non-TEAE, TEAE).

All other safety assessments will be summarized by Visit and Eye (Study Eye/Non-Study Eye).

According to the study protocol, both eyes of a patient should be treated. However, there might be the situation, that one eye will not be treated (which will, in fact, be a protocol deviation). If a safety assessment was performed in an eye, which has not been treated with study medication, it will not be included in descriptive summaries but displayed in listings. Such assessments will be flagged in the listings accordingly.

10 Overview of Tables, Listings and Figures

This section describes the TLFs per topic with variables and populations used. For the content, titles and layout of tables see the table shells, which will be added as appendix to this document.

10.1 Disposition of Patients

A disposition summary of patients includes the number (n) and percentage (%) of patients screened, screen failures, included in the Enrolled Set, included in the SAF, FAS as well as in the PPS as defined in section 7.1. Presentation will be provided by study treatment and overall. Percentages, if applicable, will be based on the total number of patients (of considered treatment group) included in the Enrolled Set. A listing will also be provided for this information on individual patient level for the Enrolled Set.

A summary of study discontinuation will be provided for the Enrolled Set including number and percentage of discontinuations study during treatment period, primary reason for study discontinuation during treatment period, discontinuations during the Follow-Up period, primary reason for study discontinuation during the Follow-Up Period as well as study completers. Moreover, number and percentages of patients who were unmasked during study will be provided. Presentation will be provided by study treatment and overall. Percentages will be based on the total number of patients (of considered treatment group) included in the Enrolled Set.

A listing will also be provided for this information added by the date of first and last study medication intake as documented on the eCRF page 'Study Drug Dosing Dates'.

For Screen failure a listing will be provided including the primary reason for discontinuation.

10.2 Protocol Deviations and Patient Eligibility

Protocol Deviations that might affect the efficacy of treatment will be reviewed during BDRM. A major protocol deviation will lead to an exclusion from the PPS.

The number of patients in the FAS who had at least one Major Protocol Deviation as well as a specific type of protocol deviation (as defined during the BDRM) will be summarized by absolute counts (n) and percentages (%) and displayed by treatment group and overall. Percentages will be based on the number of patients in the FAS.

A listing will be provided presenting all protocol deviation data for the Enrolled Set.

The eligibility of all patients for entry into the study will be assessed at the Baseline visit by the inclusion and exclusion criteria ('Inclusion Criteria' and 'Exclusion Criteria' eCRF pages). Two listing will presented including all patients of the Enrolled Set, who fail/meet at least one Inclusion or Exclusion criteria, along with all their deviating Inclusion and Exclusion responses, respectively.

10.3 Demographic and Other Baseline Characteristics

10.3.1 Demographic Characteristics

Demographic data age, gender, ethnicity as well as race will be summarized by treatment group and overall for the Enrolled Set by treatment group and overall. Demographic Data will also be listed.

10.3.2 History of Dry Eye disease and other Medical History

Summary statistics will be provided for Time since Initial Diagnosis of Dry Eye and Identification of Study Eye by treatment group and overall for patients in the Enrolled Set. A listing will also be provided with additional presentation of etiology of disease.

Other Medical History will be summarized for the Enrolled Set by treatment group and overall on a per-patient basis (i.e. if a patient reported the same event repeatedly the event will be counted only once at the specific level of display). Absolute counts (n) and percentages (%) will be presented for the number of patients with at least one Medical History event, and per SOC and per PT within SOC.

A listing presents all medical history data for the Enrolled Set.

10.3.3 Prior and Concomitant Medications

Prior and Concomitant Medications will be summarized for the Enrolled Set on a per-patient basis (i.e. if a patient reported the same medication repeatedly the medication will be counted only once at the specific level of display). Absolute counts (n) and percentages (%) will be presented for the number of patients with at least one medication, and per WHO-ATC Drug Class 2 (ATC therapeutic main class) and per WHO-DD Drug Name (Preferred Term) within WHO-ATC Drug Class 2.

A Listing will be presented for Prior and Concomitant medications of patients in the Enrolled Set providing all collected details on the eCRF.

In addition, a listing will be provided for the Enrolled set presenting additional data on the frequency of applying artificial tears as collected on the eCRF page 'Artificial Tears Monitoring' for Day 0 and Week 12.

10.4 Measurements of Exposure and Treatment Compliance

Exposure will be evaluated by summary statistics for the parameters Treated Eyes and Treatment Duration by treatment group. This analysis will be performed for the SAF. This information will be listed.

Compliance will be summarized categorical (<80%, 80-120%, >120%) for the FAS by treatment group. This information as documented on the eCRF Page 'Study Drug Dosing and Accountability' will be listed for the SAF accordingly.

Further information on compliance as recorded on the eCRF Page 'Diary Information' and 'Exposure' at Week 4 and Week 8 will be listed for the SAF.

Further information on compliance as recorded on the eCRF Page 'Patient Diary' at Week 4 and Week 8 will be listed for the SAF.

